5.2 General Concomitant Medication and Supportive Care Guidelines

Acceptable Therapy

Concomitant medications and therapies deemed necessary for the supportive care and safety of the patient are allowed. Examples include anti-diarrheal medications, antiemetics, or electrolyte supplementation.

Patients must be told to notify the investigational site staff about any new medications, herbal remedies, or dietary supplements that he or she takes after the start of the study treatment, regardless of treatment duration. All concomitant medications and significant non-drug therapies (including physical therapy, herbal or natural medications, and blood transfusions) administered during the study must be documented on the concomitant medications list.

IV hydration prior to administration of study medications or required to manage toxicity associated with any of the study medications (eg, hypotension) should be recorded on the concomitant medications list.

Required inactivated vaccinations (ie, influenza vaccine) may be administered per investigator discretion. Inactivated (non-live) vaccine(s) should NOT be administered during first 4 weeks of tebentafusp therapy or administered within 24 hours before or after tebentafusp dosing. Vaccine(s) administered during the study should be recorded on the concomitant medications list.

Treatment with hematopoietic colony-stimulating growth factors (eg, G-CSF, GM-CSF, M-CSF, or erythroid-stimulating agents) may not be initiated during the first cycle. If a patient requires an erythropoiesis-stimulating agent prior to enrollment (beginning at least 2 weeks before start of study treatment), they may continue at the same dose.

Anti-coagulant therapy is permitted if the patients are already at stable doses for > 2 weeks at time of first dose. Low molecular weight heparin can be started during the overnight observations, if discussed and approved by the Principal Investigator in advance. The international normalized ratio should be monitored as clinically indicated

per investigator's discretion. Ongoing anti-coagulant therapy should be temporarily discontinued to allow tumor biopsy according to the institutional guidelines.

Anti-hypertensives are allowed as concomitant medications; however, because transient hypotension has occurred during infusions of tebentafusp and monoclonal antibodies, treatment with anti-hypertensive therapy should be held for 24 hours before and 24 hours after tebentafusp in the first 6 weeks of treatment, and thereafter, at the discretion of the principal investigator. Medications administered as supportive care of bony metastases, including bisphosphates and denosumab, may be administered during study therapy.

Treatment with palliative radiotherapy to tumor locations to alleviate pain is acceptable during the course of the study provided that: (1) with bony lesions, no new bone lesions are noted (representing clinically significant progression of disease) and (2) only non-target lesions are radiated. Radiation of target lesions is not permitted while receiving study treatment.

Prohibited Therapy

While on study treatment, patients may not receive other additional investigational study drugs, agents, devices, chemotherapy, or any other therapies that may be active against cancer. As described above, palliative radiotherapy or surgery is allowed and bisphosphonates may be given for bone metastases. Additionally, no other therapeutic monoclonal antibodies, except for denosumab and tocilizumab if required for patient care, and no immunosuppressive medication may be administered while on this study, unless prescribed to manage toxicity as recommended in Appendix B. While systemic corticosteroid therapy will interfere with the mechanism of action of the study medications, its use is recommended in some settings. Live or attenuated vaccines are prohibited from 28 days prior to the first dose until 30 days after the final dose of the study drug.

Patients with adrenal insufficiency or patients receiving systemic steroid therapy or any other immunosuppressive medication at any dose level at Screening are excluded. Patients receiving corticosteroids may not be able to mount an appropriate physiologic cortisol response in the event of an infusion reaction with initial tebentafusp dosing. Corticosteroids and other immunosuppressives may interfere with the mechanism of action of the study drugs. The use of systemic corticosteroid therapy is permitted/recommended in the following settings: (1) infusion reactions and (2) immune-mediated toxicities and toxicity management (eg, hypotension and CRS) as directed in Appendix B (eg, hypotension not resolving with fluid support alone). Of note, patients with a pre-existing history of adrenal insufficiency are excluded from study participation. Any additional uses of systemic corticosteroid therapy during the study should be discussed with the Principal Investigator.

5.3 Duration of Therapy

Treatment may continue until one of the following criteria applies:

- Disease progression as defined by RECIST v 1.1 unless criteria for treatment beyond initial PD is met (see Section 5.3.1)
- If continuing treatment beyond initial PD, then patients must discontinue study treatment once further PD warranting treatment discontinuation is met (see Section 5.3.1)
- Initiation of alternative anti-cancer therapy including another investigational agent
- Unacceptable toxicity as defined in Appendix B or any AE that, in the opinion of the investigator, contraindicates further dosing
- Withdrawal of consent from further treatment with investigational product by the patient or the investigator
- Patient is lost to follow-up
- Patient is determined to have met 1 or more of the exclusion criteria or failed to meet all of the inclusion criteria for study participation AND continuing to receive investigational product might constitute a safety risk. Patients who fall into this category and for whom continuation of treatment is not thought to pose a safety risk, in the opinion of the investigator, may continue to receive study treatment
- Pregnancy or intent to become pregnant

At the time patients discontinue study treatment, the EOT visit should be scheduled in the appropriate window of 14 days after the last dose was administered. At this visit, all of the assessments listed for the EOT visit will be performed. If the decision to withdraw the patient occurs at a regularly scheduled visit, that date of visit may become the EOT visit rather than having the patient return for an additional visit (safety follow-up will still continue for the full 30-day observation period). An EOT disposition document should be completed at the EOT visit, giving the date and reason for stopping the study treatment.

Patients who discontinue study treatment should NOT be considered withdrawn from the study. They should return for the assessments indicated in Section 11. If they fail to return for these assessments for unknown reasons, every effort (eg, telephone, email, and registered letter) should be made to contact them. If a patient discontinues study treatment, but continues study assessments, the patient remains on study until such time as he/she completes protocol criteria for ending study assessments. At that time, the reason for study completion should be documented.

5.3.1 Criteria for Treatment Beyond Initial RECIST v1.1 Disease Progression

Clinical evidence suggests that a minority of patients treated with immunotherapies, including tebentafusp, will derive clinical benefit after an initial assessment of PD. If initial PD based on RECIST v1.1 occurs, treatment may continue according to the protocol-specified regimen provided ALL of the following criteria continue to be met:

- Absence of signs or symptoms indicating clinically significant PD

- No decline in ECOG performance status
- No impending threat to vital organs/critical anatomical sites (eg, spinal cord compression, liver function decline) requiring urgent alternative medical intervention or where continuation of study therapy would prevent institution of such intervention
- Absence of any of the investigational product discontinuation criteria

Patients are not required to continue treatment beyond initial RECIST v1.1 PD. Both the patient and the investigator must agree continuing treatment would be in the patient's best interest. Patients continuing treatment beyond the protocol-specified RECIST v1.1 PD must provide separate consent to continue treatment after an initial assessment of PD. In addition, instances where RECIST v1.1 PD is equivocal or warrants follow-up confirmation, in the judgment of the investigator, prior to continuing study treatment, consent should be obtained at the time of initial suspicion of PD with appropriate discussion of the risk:benefit of continuing study treatment with the patient.

Patients who are treated beyond initial RECIST v1.1 PD must permanently discontinue study treatment if they experience further progression warranting treatment discontinuation. Further progression warranting treatment discontinuation is defined as ANY one of the following observed at least 4 weeks after the initial PD assessment per RECIST v1.1: 1) an additional $\geq 20\%$ increase in tumor burden (sum of diameters of both target and new measurable lesions) accompanied by an absolute increase of ≥ 5 mm; 2) unequivocal PD of non-target lesions; or 3) new non-measurable lesions.

Treatment and assessments after an initial assessment of PD will continue to follow the treatment regimen. Imaging data will continue to be obtained until further progression warranting treatment discontinuation (as defined above) or criteria for discontinuation of study treatment following RECIST v1.1 PD are met.

5.4 Duration of Follow Up

Survival follow-up should be completed every 12 weeks until death, withdrawal from study, or until the end of the study is reached.

5.5 Criteria for Removal from Study

Patient must be withdrawn from the trial for the following reasons:

- Patient dies.
- Patient is lost to follow-up.
- Patient withdraws consent for any further participation including further survival follow-up.
- The end of study is reached

If none of these conditions are met, patients should continue to be followed for survival status. The reason for study removal and the date the patient was removed must be documented in the Case Report Form including death or lost to follow up.

6. DOSING DELAYS/DOSE MODIFICATIONS

All dose modifications should be based on the worst preceding toxicity. See Appendix B for management of tebentafusp-related AEs.

For tebentafusp, escalation steps during interpatient dose escalation (ie, increasing from 20 mcg to 30 mcg or increasing from 30 mcg to 68 mcg) may be delayed. Dose reductions from 68 mcg are not permitted.

Weekly tebentafusp doses may be omitted as needed for management of AE. After completing 3 months of treatment, the Investigator may permit occasional, infrequent dose omissions to accommodate holidays, vacations, and the like.

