Patients who are HLA-A*02:01-negative and ineligible to receive tebentafusp will be prospectively enrolled onto a separate study arm and treated with physicians' choice of treatment. They will also be radiographically assessed at the same schedule as patients treated with tebentafusp, if feasible, and kept on this treatment arm until progression of disease or unacceptable toxicity on the physicians' choice regimen.

Maximum Total Number of Subjects

23 patients will be on treatment arm. 24 patients will be on a physician's choice arm. This equals 47 total.

Target Population

Unresectable or metastatic clear cell sarcoma patients who are HLA-A*02:01 positive.

Anticipated Length of Study (patient enrollment period, overall length including follow-up)

5 years total: 3 years of enrollment, 1 year on treatment, 1 year follow-up

Study Drug (s)

Tebentafusp

Dosing and Administration

Tebentafusp will be administered via IV infusion on Days 1, 8, and 15 of a 21-day cycle. Treatment on C1D1 will be 20mcg, treatment on C1D8 will be 30 mcg. After this initial dosing period, beginning at C1D15 and beyond, patients are eligible to receive the full dose of 68 mcg. This escalated dose administered at C1D15 will be the dose used for the remainder of the treatment period unless dose reduction is implemented for toxicity.

Efficacy Evaluations

Radiographic assessment via CT or MR (where CT is not feasible or per the investigator's discretion) will occur at baseline and every subsequent 6 weeks through 48 weeks, and then every 9 weeks thereafter (+/- 7 days on scan date).

Tumor evaluations for the purposes of the primary endpoint are made based on RECIST v1.1. The efficacy assessments and definitions of best response and PD for the purposes of the primary endpoint of ORR described in this study are based on the RECIST v1.1 (section 11.1.4).

Safety Evaluations/ Concerns

Tebentafusp is FDA-approved for HLA-A*02:01-positive adult patients with unresectable or metastatic uveal melanoma. Patients will be monitored for AEs and toxicities will be reported per CTCAEv5.

Special warnings and precautions listed in the investigator's brochure include:

- 1) Cytokine release syndrome
- 2) Rash
- 3) Elevated liver enzymes

Other clinically relevant AEs include:

- 1) Tumor flare/pain
- 2) Elevated pancreatic enzymes
- 3) Lymphopenia

Correlative Studies

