3. Hospitalization at other days (eg, Cycle 2 and beyond) is determined at the discretion of the principal investigator based on the patient's history and tolerance for the initial doses of the study medication, with the exception of patients experiencing a treatment delay (please refer to bullet 4 below).
4. Patients experiencing a break or delay in treatment for any reason of more than 2 weeks AND with a history of a grade 3 or 4 event of hypotension with tebentafusp dosing during the first weeks of treatment will be monitored as an inpatient for the dose subsequent to the break in dosing, regardless of the timing of the break in dosing, with vital signs monitored at a minimum of every 4 hours and monitoring for at least 16 hours after dosing.

If none of the first six patients experience **Grade ≥ 2 CRS or Grade ≥ 3 infusion-reactions**, subsequent patients can be treated as an outpatient for their intra-patient dose escalation. However, all patients undergoing intra-patient dose escalation require monitoring in a facility with access to resuscitation equipment, rescue medications, and physician availability. Patients must be monitored for at least 8 hours post-end of infusion on C1D1, C1D8, and C1D15. Vital signs must be confirmed stable prior to discharge. Minimum thresholds are body temperature $< 38.2^{\circ}\text{C}$, heart rate < 110 beats per minute, and oxygen saturation 92% on room air.

Antihypertensive drugs are allowed as concomitant medications; however, because transient hypotension has occurred during infusions of monoclonal antibodies and ImmTACs, the investigators should consider reducing or not administering antihypertensives for 24 hours before and after the tebentafusp administration during at least the first 3 weeks of treatment. Appropriate management of patients, especially those with more severe hypertension, receiving medications that may cause rebound hypertension when abruptly discontinued or those who are on multiple blood pressure medications should be discussed with a cardiology consultant and the Principal Investigator.

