7.3 Warnings and Precautions

7.3.1 Cytokine Release Syndrome

Cytokine release syndrome is a class effect of all T cell engagers and is due to an immune cascade following T cell activation. The tebentafusp regimen did not mandate prophylactic corticosteroids, antihistamines, or acetaminophen prior to dosing. Cytokine release syndrome was programmatically adjudicated using the ASTCT consensus grading for CRS (Lee, 2019). As of the DCO for this IB update, 344 (88.0%) of the 505 patients who received tebentafusp monotherapy across all clinical studies, experienced an AE of CRS that was considered related to study drug.

In IMCgp100-202 Study, which forms the largest dataset of programmatically derived CRS events, approximately 89% of patients following tebentafusp administration experienced CRS.

Most patients had Grade 1 (12%) or Grade 2 (76%) CRS. The incidence of Grade 3 CRS was 0.8%. There were no Grade 4 CRS or death due to CRS. The diagnosis of CRS following tebentafusp infusion was based most frequently on pyrexia followed by hypotension and infrequently hypoxia. Other commonly observed symptoms with CRS included chills, nausea, vomiting, fatigue, and headache.

Most patients experienced CRS following each of the first 3 tebentafusp infusions, with decreasing severity and frequency. In the majority of cases, CRS started on the day of infusion. Pyrexia was noted in nearly all cases of CRS, and in these patients, an increase in body temperature generally occurred within the first 8 to 10 hours after tebentafusp infusion. Cytokine release syndrome rarely (1.2%) led to treatment discontinuation. Cytokine release syndrome should be managed per the institutional protocol for CRS. In the absence of an institutional protocol, management guidance for hypotension and CRS with fluid management and IV corticosteroids has been included in all study protocols with tebentafusp. Based on the observed toxicities during the early weeks of dosing (eg,

hypotension), specific recommendations for close observation of subjects are included in each of the clinical study protocols.

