10.5 VITAL SIGNS

Vital signs (body temperature, pulse rate, respiratory rate, and blood pressure, oxygen saturation) must be performed before dosing, and after the tebentafusp administration as indicated in Table 3 and as per institutional standards.

Vital signs should be assessed on the scheduled day, even if study treatment is being withheld. More frequent examinations may be performed at the discretion of the investigator if medically indicated and will be recorded as unscheduled assessment.

Table 2 Tebentafusp Post-dose Vital Signs Monitoring

C1D1, C1D8, C1D15 Inpatient monitoring required for all	Vital signs monitored per institutional standards at a minimum of every 4 hours.
--	--

dosings of the first six patients; if no Grade \geq 2 CRS or Grade \geq 3 infusion-reactions are seen among the first six patients, subsequent patients can be treated as outpatients
	
Patients should be monitored for at least 16 hours after dosing. Patients experiencing grade 2 or greater hypotension at C1D15 require inpatient monitoring for the subsequent/next C2D1 dose. Those experiencing grade 3 or 4 hypotension at C1D1, C1D8, or C1D15 require hourly vital signs monitoring for a minimum of 8 hours after dosing for any doses administered as an outpatient through C3D1. Patients who are permitted to receive dose escalation treatment as an outpatient must be monitored for at least 8 hours post-end of infusion on C1D1, C1D8, and C1D15. Vital signs must be confirmed stable prior to discharge. Minimum thresholds are body temperature $<$ 38.0°C, heart rate $<$ 100 beats per minute, and oxygen saturation \geq 92% on room air. Patients should be informed to reside within a 30-minute travel distance to a local emergency room. Patients will be provided a wallet card indicating their current treatment status at the time of discharge.

C2D1 Inpatient monitoring required for exception noted
	
Patients experiencing a grade 2 or greater hypotension at C1D15 must be observed as an inpatient for C2D1 dose, with vital signs performed at a minimum of every 4 hours and monitoring for at least 16 hours after dosing.

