2 At screening and C1D1, prior to dosing, a complete physical examination will be completed. From C1D8 onwards, a short physical examination will be performed. Starting with C4D1, patients will have short physical examination performed only on day 1 of the cycle and at EOT

3 Inpatient hospitalization and frequent vital signs (at a minimum of every 4 hours [\pm 30 min] or more frequently according to institutional standards) are required at C1D1, C1D8, and C1D15. Inpatient monitoring at Cycle 2 Day 1 and beyond will be determined based on the toxicity observed in the individual patient in C1D1-C1D15. Patients experiencing a grade 2 or greater hypotension event at C1D15 must be observed as an inpatient for the subsequent C2D1 dose.

4 Thyroid function studies to be completed on Day 1 of every odd-numbered cycle at Cycle 3 and beyond, as well as at EOT

5 Pregnancy testing required every 6 weeks and at EOT in all WOCBP

6 Radiographic assessment via CT or MR (where CT is not feasible or per the investigator's discretion) will occur at baseline and every subsequent 6 weeks through 48 weeks, and then every 9 weeks thereafter. Progression of disease by RECIST 1.1 within 24 weeks is required for enrollment, unless the patient has a new diagnosis of CCS.

7 Mandatory biopsies are required at baseline within 28 days of study initiation and again after two cycles of treatment at C3 (+/- 7days). Biopsy at progression will be optional.

8 Research blood will be collected at baseline (during study screening or on C1D1 prior to initiating treatment), C2D1, C3D1, C5D1, C9D1, and end of treatment.

9 Tebentafusp will be administered on the scheduled day (\pm 2 days), and consecutive infusions of tebentafusp must be administered at least 5 days apart.

10 Survival follow-up should be completed every 12 weeks until death or until the end of the study is reached.

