Grade 3 or 4	
Hold all doses of tebentafusp until returned to CTCAE Grade ≤ 1.
 
 Institute regular monitoring of liver enzymes until improving or resolved. Administer intravenous steroids (eg, methylprednisolone 0.5 to 1 mg/kg/day or the equivalent) if no improvement within 24 hours. Consider abdominal imaging and a hepatology consult for persistent elevated liver enzymes, onset of clinical signs or symptoms of liver dysfunction (eg, abdominal pain, nausea, vomiting, jaundice), or impact on liver synthetic function. For any Grade 3 elevated liver enzyme elevation, restart tebentafusp only after discussion and written approval from the Medical Monitor. 
Once elevated liver enzymes improve to NCI CTCAE Grade ≤ 1, if restarting tebentafusp, resume treatment as follows:
 
 If elevated liver enzymes occurred in the setting of Grade 3 CRS, resume at the current dose level. Resume escalation once the current dose level is tolerated. If elevated liver enzymes occurred outside the setting of Grade 3 CRS, then resume intrapatient escalation if the current dose level is less than 68 mcg; otherwise, resume treatment at the current dose level if intrapatient escalation has been completed.
Vomiting (graded per CTCAE v5.0)	
Grade 2	
 Administer antiemetic therapy as per institutional standard. Provide IV fluid support and other supportive measures for additional AEs as needed.
Grade 3 or 4	
 Consider holding all doses of tebentafusp until improvement to NCI CTCAE Grade ≤ 1. Administer antiemetic therapy as per institutional standard. Provide IV fluid support and other supportive measures for additional AEs. Consider instituting antiemetic premedication for at least the next dose (eg, ondansetron 8 mg PO/IV or equivalent).
Other Clinically Significant Adverse Events (graded per CTCAE v5.0)	
Treat according to institutional practice and for potential immune-related AEs of Grade ≥ 3 ; treatment with corticosteroids should be considered. Consult the Medical Monitor for further guidance as needed.	
Grade 3 or 4	
Study medication(s) should be permanently discontinued unless AEs improves to Grade 1 or 0, the Investigator believes the overall benefit-risk favors continued treatment, and there is agreement with the Medical Monitor that the participant may restart treatment at the current or reduced dose.

Confidential

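### Conflicting rules on dose reduction from 68 mcg, outpatient discharge thresholds and inpatient stay need to be reconciled

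*Protocol*

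**What the plan says.** **Dose reduction.** Protocol Section 6 says "Dose reductions from 68 mcg are not permitted" and refers to Appendix B for managing toxicity. The synopsis (Dosing and Administration) says that the dose reached at C1D15, which is 68 mcg, "will be the dose used for the remainder of the treatment period unless dose reduction is implemented for toxicity". In Appendix B, the row for other clinically significant adverse events of Grade 3 or 4 provides, with the Medical Monitor's agreement, that "the participant may restart treatment at the current or reduced dose".

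**Discharge after the first three doses.** Section 5.1.3 gives minimum thresholds for patients escalated as outpatients: temperature below 38.2°C and heart rate below "110 beats per minute, and oxygen saturation 92% on room air". Table 2 in Section 10.5 covers the same discharge with temperature below 38.0°C and heart rate below "100 beats per minute, and oxygen saturation" of at least 92%.

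**Setting of the first three doses.** Study Calendar footnote 3 says that inpatient hospitalization and vital signs every 4 hours "or more frequently according to institutional standards) are required at C1D1, C1D8, and C1D15". Section 5.1.3 says that if none of the first six patients has Grade 2 or higher cytokine release syndrome (CRS) or a Grade 3 or higher infusion reaction, "subsequent patients can be treated as an outpatient for their intra-patient dose escalation". Section 5 and Table 2 carry the same conditional release.

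**Antihypertensives.** Section 5.1.3 asks investigators to consider reducing or omitting them for 24 hours either side of dosing, for at least the first 3 weeks. Section 5.2 says they should be held over the same window for the first 6 weeks.

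**The concern.** These are current operative texts, and the protocol does not say which prevails where they differ. With about four centers (Section 12.1.4), one site may follow the synopsis or Table 2 and another Section 6 or Section 5.1.3. Two patients in the same condition could then be dosed or discharged differently, and whether a protocol deviation has occurred would be ambiguous.

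The rules govern the period around the first infusions, which is where Sections 5 and 7.3.1 place most of the CRS, hypotension and other moderate-to-severe toxicity. The first stake is patient safety. The second is that exposure and safety summaries could mix patients handled under different rules. That second effect is plausible, but the documents do not show it.

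**Working it through.** The protocol states no figure on this point that could be reproduced. The check sets the texts side by side.

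| Topic | One text | Another text | Can both be applied as written? |
|---|---|---|---|
| Reduction from 68 mcg | Section 6: not permitted | Synopsis: foreseen for toxicity | No. A reduction made under the synopsis breaches Section 6 |
| Restart after other Grade 3 or 4 events | Section 6: not permitted from 68 mcg | Appendix B, residual row: current or reduced dose | Only if the row is read as excluding patients at 68 mcg, which it does not say |
| Discharge temperature | 5.1.3: < 38.2°C | Table 2: < 38.0°C | No, for readings from 38.0°C up to but not including 38.2°C |
| Discharge heart rate | 5.1.3: < 110 bpm | Table 2: < 100 bpm | No, for readings from 100 up to but not including 110 bpm |
| Setting, doses 1 to 3 | Footnote 3: inpatient, no exception | 5, 5.1.3, Table 2: outpatient allowed after six patients if the condition is met | No, once the condition is met |
| Antihypertensives | 5.1.3: consider, at least 3 weeks | 5.2: should be held, 6 weeks | Yes. Strength and duration differ, but at least 3 weeks does not exclude 6 |

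**Size of the discharge conflict.** 38.2 − 38.0 = 0.2°C, and 110 − 100 = 10 bpm. A patient at 38.1°C, or at 105 bpm, with all other signs acceptable meets Section 5.1.3 and fails Table 2.

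**Side check: how often the outpatient branch might open.** This is not one of the contradictions. It only shows how often the discharge and setting conflicts could matter.

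- Input: Section 7.3.1 reports for the IMCgp100-202 uveal melanoma study "Most patients had Grade 1 (12%) or Grade 2 (76%) CRS", with Grade 3 at 0.8% and no Grade 4. Grade 2 or higher is 76% + 0.8% = 76.8%.
- Assumptions: this rate carries over to clear cell sarcoma, and the six patients are independent.
- Formula: P(no Grade ≥ 2 CRS in six patients) = (1 − p)^6.
- p = 0.768: 0.232^6 = 0.00016.
- p = 0.50 (assumed): 0.50^6 = 0.016.
- p = 0.30 (assumed): 0.70^6 = 0.118.

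The release also needs no Grade 3 or higher infusion reaction, so under each assumed rate these figures are upper limits on the chance of release.

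**The case against.** **Appendix B mostly agrees with Section 6.** The event-specific rows that address patients at 68 mcg (pruritus, rash, CRS, liver enzymes) keep that dose. The reduced dose appears only in the residual row, which does not mention 68 mcg and could be meant for the lower steps. This stands in part: the Appendix B conflict is the weaker one. It does not touch the synopsis, whose sentence is about the 68 mcg dose itself.

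**Conduct that meets the narrower wording also meets the wider.** This is true of the discharge thresholds and of the inpatient stay. It shows that a site could satisfy both texts, but the protocol does not say that the narrower one governs, and a site relying on Section 5.1.3 alone has no signal that Table 2 differs.

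**Footnote 3 is only a calendar summary.** The main text states the conditional release explicitly and consistently. This stands, so the footnote is a supporting item and not the main conflict.

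**The release condition.** From the CRS rates in Section 7.3.1, a reader might infer that the condition itself contradicts the protocol. The documents do not support that. The condition is worded alike in Sections 5 and 5.1.3 and Table 2. Section 7.3.1 reports another study and sets no rule, and a strict condition is a clinical design choice. Carrying the rate over is also uncertain: Section 5.1.2 attributes the enhanced toxicity in uveal melanoma to high gp100 expression, lymphocyte trafficking and extent of disease, and no document gives a CRS rate for clear cell sarcoma. Moreover, if the outpatient branch rarely opens, the discharge and setting conflicts seldom apply. The near-zero probability therefore lowers their practical weight.

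**Conclusion.** The protocol contains two clear conflicts in safety conduct: whether the 68 mcg dose may be reduced, and which vital-sign limits permit outpatient discharge after the first three doses (0.2°C and 10 bpm apart). Footnote 3 on inpatient stay supports the point, and the antihypertensive guidance is a difference of wording in strength and duration.

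The dose-reduction conflict can affect any patient who reaches 68 mcg. The discharge and setting conflicts arise only if outpatient escalation opens. The chance of that is about 0.0002 if the uveal melanoma CRS rate carries over, and 0.016 or 0.12 at assumed rates of 50% or 30%.

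A reader might go further and infer that sites cannot apply any single rule, or that deviations are impossible to judge. That is too strong: several of the texts can be satisfied together, and ambiguous is the accurate word. Nor does anything here affect the 24-week endpoint, the two-stage design or its error rates. The point still warrants correction because it concerns patient safety and rests on the protocol's own text.

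**What to change.** Amend the protocol so that each rule is stated once and cross-referenced elsewhere:

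- Reconcile Section 6, the synopsis and the residual row of Appendix B on whether a reduction from 68 mcg exists. If the Appendix B row is meant only for certain dose levels, say so there.
- Reconcile Section 5.1.3 and Table 2 on the discharge thresholds for temperature and heart rate.
- Reconcile Study Calendar footnote 3 with Sections 5 and 5.1.3 and Table 2 on who must be an inpatient for the first three doses.
- Reconcile Sections 5.1.3 and 5.2 on the strength and duration of the antihypertensive guidance.

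Which rule applies in each case is for the clinical team, and this review takes no view. The cost is amendment wording, with no added patients or procedures and no change to the statistical design.
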